
Furthermore, our expectation is that this difference will be most apparent at 48 hrs. as discussed above with a reduction in narcotic requirements greater than 40% in the continuous catheter TAP group vs. standard single shot Bupivacaine TAP (4.1 mg +/- 3 mg vs. 2.4 mg +/- 1.3 mg Dilaudid). This is based on the assumption that the effects of the local anesthetic control TAP (single shot Bupivacaine) may last up to 24 hrs. At 72 hrs, prior studies, although limited, have not shown a significant difference between TAP block and placebo groups.

c Study Objectives

Primary Aim

The primary aim is to evaluate for any significant difference total post-operative narcotic requirements (Dilaudid) required over 48 hrs. in the continuous catheter TAP block arm vs. the single shot Bupivacaine TAP arm and again the slow release Liposomal Exparel® TAP arm vs. the single shot Bupivacaine TAP arm.

Secondary Aim

The secondary aim will be to evaluate for any significant difference in narcotic requirements at other endpoints such as 24 hrs and at 72 hrs. As discussed before, current studies do not show a significant difference when extrapolated out at those end points, albeit there is very little data at 72 hrs. Other quality indicators of recovery in the three arms such as Visual Analog Scores (VAS) are expected again to be most significantly different at 48 hrs. Other quality measures that will be recorded include incidence and severity of post-operative nausea and vomiting (PONV), time to ambulation, and patient satisfaction with post-operative pain control.

Rationale for the Selection of Outcome Measures

Outcome measurements are based on the assumption that narcotic requirements (i.e. intravenous Dilaudid Patient-Controlled Analgesia [PCA] use) are inversely related to patient satisfaction in regards to their post-operative pain. Additional factors such as VAS, ambulation, performance of daily activities, and anti-emetic pharmaceutical requirements have been chosen as quality indicators in regards to post-operative pain control and dependence on narcotics.

D Investigational Agent

This investigation will use three FDA-approved techniques:

- Bilateral Continuous TAP block via Catheter (One-time bolus of Bupivacaine 0.25% x 20ml per side followed by continuous infusion of Ropivacaine 0.2% 7 ml/hr. per side x 48 hrs.);
- Single Injection TAP block with Exparel® (One-time bolus of Bupivacaine 0.25% x 20 ml followed by Exparel 133 mg per side); and

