Subjects will be consented using a current informed consent form that has been approved by the respective study site's Institutional Review Board. Subjects will be allowed adequate time to read the informed consent, discuss the consent with study staff and others (e.g., family members, friends, or any of their health care providers), and have their questions answered prior to signing the informed consent. In some cases, a site may not accrue study subjects but serve as a data analysis site so informed consent may be waived for that site.

Site-specific recruitment plans and consent process are outlined in Attachment L1.

E2.e Randomization Method and Blinding

Subjects that would normally be selected to receive a TAP block will be randomly assigned into one of the three arms. A random number generator will be used to generate an equal proportion of responses of the three arms. These responses will be sealed in envelope. The anesthesia provider will be allowed to open the envelope and become aware of the selected arm after the initiation of anesthesia (this would include the administration of a pre-medication or initiation of general anesthesia). Complete blinding is impossible to staff given the visual presence of a catheter in some groups versus the lack of catheters in other groups. In addition, the agent Exparel® has a milky color that is obvious to the anesthesia provider injecting it. However, the nursing staff on the floor will not be made aware of the use of Exparel® versus Bupivacaine in the single injection arms.

E2.f Risks and Benefits

i Risks

Potential physical risks include:

TAP block is a relatively low risk regional anesthesia technique with a long track record. However, any injection or insertion of a catheter into the body carries a slight risk of bleeding, bruising at injection or insertion site, and infection at injection or insertion site. Risks particular to an injection of a local anesthetic into the abdominal area would be bowel perforation, local anesthetic toxicity, and drug allergy. These risks are unlikely and similar to an abdominal paracentesis. Furthermore, the author is unaware of any episodes of bowel perforation from the administration of a TAP block.

The following are side effects have been seen with the local anesthetics Bupivacaine and Ropivacaine:

- Low blood pressure
- Nausea and/or vomiting
- Slow heartbeat
- Fever
- Pain
- Post-operative complications
- Low blood hemoglobin (anemia)

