Based on the above hypothesis this study will be considered successful in demonstrating superior efficacy relative to control if consumption of opioids postoperative is significantly less among patients randomized to receive a

continuous TAP block via the ON-Q[®] system compared to the patients randomized to receive a single TAP injection of Exparel (liposomal bupivacaine) or single TAP injection of Ropivacaine to treat postoperative pain. However, a finding of no difference between the continuous catheter technique and the Exparel arm would also be considered beneficial to the advancement of post-operative pain control techniques because it would demonstrate similar post-operative pain control can be achieved without the extra time and skill required to place a catheter.

Statistical Methods

Sample Size

The main objective of study is to compare total opioid consumption between the single shot TAP group and the Exparel TAP group with a parallel design. Based on previous studies and internal pilots, the mean total opioid consumption (standard deviation) was 4.1 mg (SD 3 mg) in single shot group and 2.4 mg (SD 1.3 mg) in Exparel TAP group. For the sample size calculation, a standard deviation of 3 is used as a conservative estimate. To detect a difference in mean opioid consumption between treatment groups, 4.1 mg vs. 2.4 mg, a sample size of 49 patients per arm is required to achieve 80% power with a significance level of 0.05 using a two-sided t-test or Wilcoxon rank-sum test depending on normality test. A secondary aim is to examine a difference in mean opioid consumption between the single shot TAP group and continuous TAP group. Allowing for a 10% dropout rate, a total of 159 participants with 53 participants in each arm will therefore need to be recruited into the study. It anticipated that approximately 8 participants per week will be enrolled into this study, thus the estimated accrual time is around 1 year.

Statistical Analysis Plan

All analyses will be conducted on patients following an intention-to-treat principle, including all randomized participants enrolled in three arms, in case of relevant non-compliance to the treatment and/or impossibility to evaluate the endpoints, a per-protocol analysis will also be performed, together with an analysis of non-compliance/non-evaluation.

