Patient characteristics and outcomes data will be summarized by cross-tabulation (categorical variables), quartiles (median, ordinal variables), and mean and standard deviation (continuous variables). Comparisons between groups will use Chi-square test or Fisher's exact test as appropriate for categorical variables and t-test or Wilcoxon rank-sum test as appropriate for continuous variables.

Analyses of primary outcome will examine differences in mean opioid consumption between the single shot TAP group and the Exparel TAP group. Analyses of secondary outcomes will examine differences in mean opioid consumption between the single shot TAP group and continuous TAP group. Treatment groups will be compared using a

student's t-test if data are normal distributed or Wilcoxon rank-sum test if not normal distributed.

The differences in mean opioid consumption across three groups (single shot TAP, continuous TAP, and Exparel TAP) will be examined with a test of means between groups using one-way analysis of variance (ANOVA). A comparison between continuous TAP and Exparel TAP will be performed. A t-test will be used if the observations in each trial arm are normally distributed; if non-normally distributed, then rank-based methods such as Wilcoxon rank-sum test will be employed.

All tests will be two-sided.

The overall incidence of serious adverse events and adverse events and number and proportion of patients reporting such events will be summarized by treatment group. Adverse events will be tabulated and summarized by the number and percentage of subjects who experienced the event.

Missing Outcome Data

Analysis will be conducted as described in prior section. Missing data will not be included in the analysis; however, may lead to an increase in patients recruited into one or more study arms.

Unblinding Procedures

This study is not blinded because it will be obvious to all care givers whether or not the patient received a continuous block with catheters or not.

H Data Handling and Record Keeping

Confidentiality and Security

Data will be collected on the data collection forms located in Attachment L9 and entered into the Oncore ERM study management system.

Data collection forms will be stored at each respective study site within a locked cabinet in a locked research office.

The Oncore ERM study management system is a secure web-based management system that is password-protected. Access to data is role-specific.

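### The three-group ANOVA and the Student's t-tests pool variances although the planning SDs are 3 mg and 1.3 mg; naming the Welch forms is a cheap, minor improvement

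*Combined protocol and SAP*

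**What the plan says.** Section G, Statistical Analysis Plan, sets out these tests of opioid consumption:

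- Single shot versus Exparel (primary) and single shot versus catheter (secondary), each by Student's t-test, or by Wilcoxon rank-sum if data are not normal.
- All three arms together, as a test of means "using one-way analysis of variance (ANOVA").
- Catheter versus Exparel, by t-test or a rank-based method.

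"All tests will be two-sided". No unequal-variance form is named and no check of variances is described.

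The planning figures are unequal in spread. Section G, Sample Size, gives "4.1 mg (SD 3 mg) in single shot group and 2.4 mg (SD 1.3 mg) in Exparel TAP group". Section B, Rationale for this Study, gives the single shot versus catheter contrast as "4.1 mg +/- 3 mg vs. 2.4 mg +/- 1.3 mg Dilaudid". For the sample size alone, "a standard deviation of 3 is used as a conservative estimate".

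Allocation is meant to be equal (section E2.e: "A random number generator will be used to generate an equal proportion of responses of the three arms"), with "Allowing for a 10% dropout rate, a total of 159 participants with 53 participants in each arm".

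**The concern.** A pooled-variance test takes the arms to have the same spread. Here the planning SDs imply a variance ratio of (3/1.3)² = 5.3 between single shot and either continuous-release arm. Two things follow. With three groups, equal arm sizes do not fully protect the ordinary F test. With unequal arm sizes, both the F test and the pooled t-test drift from their nominal level, in a direction set by whether the more variable arm is the smaller or the larger.

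Final arm sizes are not guaranteed to be equal. Section G, Missing Outcome Data, leaves out missing values and allows added recruitment to particular arms. Section E, Early Withdrawal of Subjects, allows failed blocks to be replaced, and allows patients whose catheter could not be placed to be counted with the single shot arm. What is at stake is the calibration of the three-group p-value and, if arms end unequal, of the pairwise t-tests, including the primary one.

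**Working it through.** **Inputs.** SDs 3 / 1.3 / 1.3 mg (single shot / Exparel / catheter) and means 4.1 / 2.4 / 2.4 mg, from sections B and G; 49 evaluable or 53 recruited per arm, from Sample Size. The 5% level is stated only for the sample size and is assumed here for the ANOVA.

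**The plan's own figure.** With a common SD of 3 mg and a difference of 4.1 − 2.4 = 1.7 mg, n = 2 × 3² × (1.960 + 0.842)² / 1.7² = 18 × 7.85 / 2.89 = 48.9, so 49 per arm. This agrees with "a sample size of 49 patients per arm is required to achieve 80% power with a significance level of 0.05".

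**ANOVA at equal arms, large-sample check.** Under equal means the between-arm mean square (scaled by arm size) is half the sum of two independent squared normal terms. Their variances are:

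- single shot against the average of the other two: (2/3) × (9 + 1.69/2) = 6.563
- Exparel against catheter: 1.69

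The within-arm mean square tends to (9 + 1.69 + 1.69)/3 = 4.127. So F behaves like 0.795·Z₁² + 0.205·Z₂², since 6.563/(2 × 4.127) = 0.795 and 1.69/(2 × 4.127) = 0.205. With equal SDs both weights would be 0.5. The weights still sum to 1, so F is right on average, but its upper tail is heavier. The chance of exceeding the nominal 5% point, 5.991/2 = 2.996, is 6.3%.

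**t-test, single shot versus Exparel.** Compare the true variance of the mean difference with what pooling estimates:

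- 49 v 49: both equal (9 + 1.69)/49 = 0.218; ratio 1.00.
- 45 v 53: true 9/45 + 1.69/53 = 0.232; pooled [(44 × 9 + 52 × 1.69)/96] × (1/45 + 1/53) = 5.040 × 0.0411 = 0.207; ratio 1.12, so the test is too liberal.
- 60 v 45: true 9/60 + 1.69/45 = 0.188; pooled [(59 × 9 + 44 × 1.69)/103] × (1/60 + 1/45) = 5.877 × 0.0389 = 0.229; ratio 0.82, so it is conservative.

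**Type I error by simulation** (normal data, equal means, SDs 3/1.3/1.3, nominal 5%, single shot listed first):

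| Arm sizes | Ordinary ANOVA | Welch ANOVA |
|---|---|---|
| 49/49/49 | 6.4% | 5.0% |
| 53/53/53 | 6.4% | 5.0% |
| 45/53/53 | 8.0% | 5.0% |
| 53/48/48 | 5.6% | 5.0% |
| 60/45/45 | 4.1% | 5.0% |
| 49/49/49 with SDs 3/3/3 | 5.0% | 5.0% |

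| Arm sizes, single shot v Exparel | Pooled t | Welch t |
|---|---|---|
| 49 v 49 | 5.1% | 5.0% |
| 45 v 53 | 6.5% | 5.0% |
| 60 v 45 | 3.2% | 5.0% |

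**Skewed data** (assumption: common mean 3 mg, same SDs, 49 per arm). Ordinary ANOVA 7.0% (gamma) and 7.8% (lognormal); Welch 5.8% and 6.8%.

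**Kruskal-Wallis** at 49 per arm, same SDs and equal means: about 6% with normal data, and about 40% with the gamma data above, because it does not test means.

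**Power at the planning values, 49 per arm.** Three-group test: about 97% ordinary, 92% Welch. Pairwise single shot versus Exparel: about 95% with either form.

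**The case against.** The strongest reply is that nothing hangs on the ANOVA. The primary and secondary analyses and the success criteria in section G are comparisons between particular arms, and no pairwise test is made conditional on the global one. This stands. A reader might infer that the trial's main result carries an inflated error rate; at the planned equal arms the documents do not support that, since the pooled primary t-test is at 5.1%.

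Second, it is tempting to say flatly that the ANOVA's error rate exceeds 5%. That needs the SDs to differ even when the means are equal. The plan quotes its SDs alongside different means, and the smaller SD goes with the smaller mean. If the arms shared one distribution, the error would be 5.0%. The direction also depends on final sizes. Nothing in the documents predicts a smaller single shot arm, and counting failed-catheter patients with single shot would enlarge it. This stands too, so the figures must be read as conditional.

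Third, one might claim that the three-group test has no non-normal alternative. The same paragraph goes on to allow rank-based methods, with Wilcoxon as an example. It follows the catheter versus Exparel sentence and its parametric option is a t-test, so its reach is unclear, but a gap is not shown.

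Fourth, one-way ANOVA as a label does not exclude Welch's form. True, but the unqualified name normally means the pooled test, and the pairwise test is named as Student's. Nor does the common SD of 3 mg claim equal variances: it is a conservative choice for the sample size.

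**Conclusion.** The point holds as a minor one. Under the plan's own SDs, with normal data and equal means, the supporting ANOVA runs at about 6.4% at the planned equal arms, an excess of 1.4 percentage points. It ranges from about 8% (45/53/53) to about 4% (60/45/45) as the single shot arm ends smaller or larger. The pooled primary t-test is essentially sound at equal arms and ranges from 6.5% (45 v 53) to 3.2% (60 v 45) otherwise. These arm sizes are illustrations, not predictions. The result rests on the SDs staying at 3 and 1.3 mg under equal means and on a 5% level for the ANOVA; with equal SDs the problem vanishes.

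**What to change.** In section G, Statistical Analysis Plan, name Welch's one-way ANOVA for the three-group test and the Welch t-test wherever Student's t-test now stands. Both hold about 5% for normal data whichever arm ends larger. For strongly skewed data the protection is partial (5.8% to 6.8% in the cases tried for the three-group test).

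Do not offer Kruskal-Wallis as the remedy for unequal variances: it is also inflated and it answers a different question from a test of means. If a rank-based alternative is wanted for non-normal data, say explicitly whether it covers the three-group test and what hypothesis it addresses.

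The cost is a change of wording, with no extra patients or data. Three-group power at the planning values falls from about 97% to about 92%; the pairwise comparison loses almost nothing.

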Subjects may be withdrawn from the study early due to complications secondary to the surgery itself such as sepsis, bowel dysfunction unrelated to narcotic use, and the need for further exploratory surgery.

Catheter dysfunction due to dislodgment or severe leakage may also precipitate early withdrawal from the study. Bleeding, infection, or need to anti-coagulate may cause premature need to remove the catheters from the patients. In these cases, the data will continue to be recorded as in the other arms; however, time of catheter removal will also be recorded.

Failure to perform an adequate block will also cause withdrawal from the study. Reasons for said failure would include: inability to visualize TAP space on ultrasound and surgical site preventing use of bilateral TAP block.

Failure to place catheter after successful bolus of local anesthetic would move patients from the CTAP group to an un-randomized single shot Bupivacaine arm. Patients will be followed until completion of the study. This data may be analyzed separate or as part of the single shot Bupivacaine group.

Failed block is a withdrawal prior to first study follow up; these patients would need to be replaced or moved to an open un-randomized arm.

Subjects may also be withdrawn from the study if at any time it is determined that they did not meet inclusion exclusion criteria.

iii Subject safety

iv Non-compliance with study visit schedule or study regimen

Subjects may be involuntarily exited from the study for failure to comply with the protocol, failure to attend follow-up visits, or for other reasons. The investigator shall arrange for an exit visit and complete the case report form for the subject to the extent there is data available.

Subjects may voluntarily withdraw from the study at any time without reason. The investigator shall make an effort to obtain an exit visit and complete the case report form for the subject to the extent there is data available. The investigator cannot require that an exit interview take place.

E2.g Data Collection and Follow-up for Withdrawn Subjects

- 1) Reason for withdrawal from study (i.e. block failure, catheter failure, drug toxicity, sepsis, patient request)
- 2) Day of withdrawal from study

Study Drug/Device

E3.a Description

The ON-Q[®] device is considered a non-significant risk device which has been marketed for postoperative pain management since 1998.

Description of Device:

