Randomization will occur following the consent process and prior to surgery. The on-site personnel will manage the randomization. A random number generator will be used to assign patients to one of three arms and the anesthesia provider will be unaware of which arm the patient is assigned to until after initiation of anesthesia (see section E2.e).

E3.c Preparation and Administration of Study Drug

Patients in the single shot arms (Bupivacaine 0.25% and Exparel) will receive bilateral bolus injections of the local anesthetic t prior to extubation (waking up from General Anesthesia). Patients in the continuous catheter arm will also receive a bolus injection of local anesthetic prior to the placement of the catheter. Those patients will also receive a pump.

- 1) Bupivacaine 0.25% Arm: A total of 60 ml Bupivacaine 0.25% from two 30 ml vials will be pre-drawn up via 60 ml Syringe. The syringe will be connected and a 10ml flush syringe containing 10ml 0.9 NS will be connected to the end of an IV extension set via a 3-way stopcock and luer lock connections. The Bupivacaine 0.25% syringe will also be connected to the stopcock. The distal end of the IV connection will be maintained sterile and will be connected to the injection needle. Then the procedure is as follows: Step 1) The entire setup will be flushed with 0.9NS via flush syringe. 2) The TAP space will be located under ultrasound guidance and verified by using the 0.9% NS flush syringe. Once in the TAP space, 30 ml Bupivacaine 0.25% will be injected into the TAP space (This dose will be decreased to 25ml for patients under 70 kg). Steps 2 and 3 will be repeated on the opposite side TAP block.
- 2) Exparel Arm: The entire contents of one 20 ml Exparel vial (266 mg) will be drawn up 20 ml syringe. 40ml Bupivacaine 0.25% will be pre-drawn into 2x 20 ml syringes and connected to a stopcock. The syringe containing the Exparel solution will also be connected to the stopcock. The distal end of the IV connection will be maintained sterile and will be connected to the injection needle. Procedure Step: 1) The entire setup

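### The missing-data rule permits extra recruitment into selected arms without requiring that the added patients be randomised, with concealment, through the equal three-arm list

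*Combined protocol and SAP*

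**What the plan says.** Section G, Missing Outcome Data, first refers back to the preceding analysis section and then states: "Missing data will not be included in the analysis; however, may lead to an increase in patients recruited into one or more study arms". Nothing there or elsewhere says how the added patients are allocated, who decides, what amount of missing data triggers the increase, or how many may be added.

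The general allocation rules are these:

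- E2.e: "Subjects that would normally be selected to receive a TAP block will be randomly assigned into one of the three arms", and "A random number generator will be used to generate an equal proportion of responses of the three arms". Assignments are in sealed envelopes, and "The anesthesia provider will be allowed to open the envelope and become aware of the selected arm after the initiation of anesthesia".
- E3.b: randomisation follows consent and precedes surgery. "The on-site personnel will manage the randomization", and "the anesthesia provider will be unaware of which arm the patient is assigned to until after initiation of anesthesia".
- Statistical Methods, Sample Size: 49 patients per arm are required, then "Allowing for a 10% dropout rate, a total of 159 participants with 53 participants in each arm".

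The Analysis Plan describes the trial as open. The Statistical Analysis Plan specifies intention-to-treat on all randomised participants.

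**The concern.** The sentence attaches extra recruitment to arms, not to the trial as a whole. A list that yields equal proportions of three arms, taken in order, cannot enlarge one chosen arm. Carrying out the rule for one or two arms therefore needs some other allocation procedure, and the plan supplies none.

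In the plainest case, one arm is topped up after the envelopes are used. Whoever approaches the patient then knows the arm beforehand, so inclusion can depend on expected opioid need. There is room for that: the data form lists procedures from ileostomy reversal to HIPEC, and no stratification is described. The added patients would also be compared with patients randomised earlier, so any change over time in case mix or care falls on one arm only. Later analysis cannot reliably undo this.

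**Working it through.** **Which readings of the rule fit the randomisation sections**

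| How extra patients are added | Random and concealed? | Equal proportions (E2.e)? | Concurrent controls? |
|---|---|---|---|
| All three arms, same list | Yes | Yes | Yes |
| Extra envelopes for one arm shuffled into the remaining stack during enrolment | Yes | No | Yes |
| Two arms only, after main enrolment | Between those two only | No | Third arm has none |
| One arm only, after main enrolment | No | No | None |

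Only the first row agrees with E2.e and E3.b throughout. The missing-data sentence allows all four.

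**The plan's own sample size**

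Inputs from Statistical Methods, Sample Size: means 4.1 and 2.4 mg (difference 1.7 mg), SD 3 mg, two-sided alpha 0.05, power 80%.

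- Normal approximation: n = 2 × [3 × (1.960 + 0.842) / 1.7]² = 48.9, so 49 per arm. The stated figure is reproduced. The exact t-test gives 49.9, so 50.
- Evaluable patients with 53 per arm and 10% loss: 53 × 0.9 = 47.7. Power is then about 78% (t-test) to 79% (normal approximation).
- Shortfall against 49: 49 − 47.7 = 1.3, so about 2 added patients per arm restore the target. Replacing every loss means about 53 × 0.10 = 5.3, so 5.

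The statistical need for a top-up at the planned loss is therefore small.

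**Possible shift in the arm mean**

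Shift = k × s / n, where k is the number of non-randomised added patients, s the difference between their mean and that of the randomised patients, and n the number analysed in the arm. The plan gives no value for s; 0.5 to 1 SD is an assumption. The planned SD is 1.3 mg for the Exparel arm (Sample Size) and the catheter arm (Rationale for this Study), and 3 mg for the single-shot arm.

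| k, n | SD | s (mg) | Shift (mg) | Share of 1.7 mg |
|---|---|---|---|---|
| 5, 53 | 1.3 | 0.65 to 1.3 | 0.06 to 0.12 | 4% to 7% |
| 5, 53 | 3 | 1.5 to 3 | 0.14 to 0.28 | 8% to 17% |
| 2, 49 | 1.3 | 0.65 to 1.3 | 0.03 to 0.05 | 2% to 3% |

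For example, 5 × 0.65 / 53 = 0.061 and 5 × 3 / 53 = 0.283; 0.283 / 1.7 = 17%.

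**Possible effect on type I error**

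With 49 analysed per arm and SD 3, the standard error of the difference is 3 × √(2/49) = 0.606 mg. For bias b = k × s / 49, the two-sided rejection rate under no true difference is 1 − Φ(1.96 − b/0.606) + Φ(−1.96 − b/0.606).

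- k = 5, s = 1.0: b = 0.10 mg, 5.3%.
- k = 5, s = 1.7: b = 0.17 mg, 5.9%.
- k = 5, s = 3.0: b = 0.31 mg, 8.0%.
- k = 10, s = 3.0: b = 0.61 mg, 17.3%.

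The last line shows what the absence of a cap allows. It is not a forecast.

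**The case against.** The strongest reply is that the sentence is conditional and incomplete, not an instruction to abandon randomisation. An increase is only possible, and one or more arms includes all three. E2.e and E3.b make no exception for added patients. Where the plan means patients outside the randomisation it says so: under Early Withdrawal of Subjects, for failed blocks, "these patients would need to be replaced or moved to an open un-randomized arm". The intention-to-treat set is defined by randomisation, so patients assigned directly to an arm would, read literally, fall outside it. One arm can also be enlarged while allocation stays random and concealed, by shuffling extra envelopes into the unused stack.

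Most of this stands, and it limits the point to what the rule permits. It does not remove the gap. The shuffled-stack method is not described and breaks the stated equal proportions, and nothing in the plan excludes a single-arm top-up after enrolment.

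A reader might infer more than the documents support:

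- That late patients will enter a chosen arm unconcealed. The text says neither that they are late nor that they bypass the envelopes.
- That the catheter arm is the likely one to be topped up. Under Early Withdrawal of Subjects, data continue to be recorded after early catheter removal, and patients whose catheter could not be placed are followed to completion. Those failures need not produce missing totals.
- That the 10% allowance already covers the losses, so the rule compensates twice. It does not quite: 47.7 is below 49.
- That a 3 mg selection effect applies to every arm. A downward shift of that size is impossible from a mean of 2.4 mg. SD 3 is the single-shot figure.
- That recruitment would be extended after looking at opioid results by arm. The stated trigger is missing data only.

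**Conclusion.** The point holds as a gap in a stated rule. Missing outcomes may trigger recruitment into selected arms of an open trial, and no section requires the added patients to be randomised 1:1:1 with concealment. If a single arm is topped up after main enrolment, those patients are neither randomly nor concealedly allocated and lack concurrent controls. If the ratio is altered during enrolment, allocation stays random but is no longer in the equal proportions of E2.e.

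At the planned loss the numerical effect is modest: about 4% to 17% of the 1.7 mg design difference for 5 added patients in an arm of 53, and less if only the 2 needed to reach 49 are added. These sizes rest on an assumed selection effect of 0.5 to 1 SD, and the upper end on SD 3. The case for correcting the rule is that it is uncapped, any resulting bias is hard to repair in analysis, and little power is gained by keeping it.

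**What to change.** In section G, Missing Outcome Data:

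1. Delete everything after the semicolon in the quoted sentence.
2. State that patients with missing data are not replaced arm by arm.
3. State that any extension of enrolment is decided on the pooled number of missing outcomes only, up to a maximum total N fixed in advance.
4. State that every added patient takes the next sealed envelope from the same 1:1:1 three-arm list, opened as E2.e and E3.b describe.

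The cost is a short text change. The downside is that evaluable numbers may be slightly unequal across arms. If the sponsor prefers to allow for loss in advance, 49 evaluable per arm at 10% loss needs 49 / 0.9 = 54.4, so 55 per arm (165 in total).
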